18.3. ECG EVALUATIONS

Results from the central ECG (Electrocardiogram) Reading Centre will be included in the reporting of this study.

Frequency and percentage of overall assessment of ECG (investigator's judgment) will be presented i.e. the percentage of patients in categories such as normal, abnormal/not clinically significant and abnormal/clinically significant will be summarized. A Fisher's exact test will be performed between the treatment groups.

18.4. VITAL SIGNS

The following Vital Signs measurements will be reported for this study:

- Sitting Systolic Blood Pressure (mmHg)
- Sitting Diastolic Blood Pressure (mmHg)
- Pulse Rate (bpm)
- Respiratory Rate (breaths/min)
- Temperature (°C)

Document: \sasdata\Mylan\Insulin_glargine\SYA22825\Biostatistics\Documentation\SAP\MYL-1501D-3004_SAP_Final_2_0_clean.doc

Author: [name]

Version Number:

2.0

Version Date:

18OCT2018

Template No: CS_TP_BS016 Revision 4
Effective Date: 01Apr2016

Reference: CS_WI_BS005

Analysis Plan Template

- Weight (kg)

The following summaries will be provided for vital signs data:

- Actual and change from baseline by visit. Descriptive summaries will be presented for the actual and the changes from baseline at each visit. Changes from baseline will be analyzed using the same MMRM model than the primary efficacy variable, but without any imputation. LSMeans for each treatment group and associated SE/2-sided 95% CI will be derived. Differences in LSMeans will be calculated with the SE, 95% CI and p-value.
- Incidence of potentially clinically significant vital signs. The number of patients and percentages will be provided for each treatment group at each visit and overall visit (patient will be counted as clinically significant if at least one clinically significant occurred in all the visits. Fisher exact test will be performed between the treatment groups.
- Listing of patients meeting markedly abnormal criteria

18.4.1. POTENTIAL CLINICALLY SIGNIFICANT CHANGES

Potential clinically significant Vital Signs measurements will be identified in accordance with the following predefined markedly abnormal criteria:

Variable	Unit	Low	High
SBP	mm Hg	≤ 90 mmHg AND change from baseline ≤ -20 mmHg	≥ 180 mmHg AND change from baseline ≥ 20 mmHg
DBP	mm Hg	≤ 50 mmHg AND change from ≤ -15 mmHg	≥ 105 mmHg AND change from baseline ≥ 15 mmHg
Heart rate	Bpm	≤ 50 bpm AND change from baseline ≤ -15 bpm	≥ 120 bpm AND change from baseline ≥ 15 bpm
Body temperature	°C	NA	≥ 38.3 °C AND change from baseline ≥ 1.1 °C
Weight	Kg	percentage change from baseline ≤ -7.0 %	percentage change from baseline ≥ 7.0 %

Document: \sasdata\Mylan\Insulin_glargine\SYA22825\Biostatistics\Documentation\SAP\MYL-1501D-3004_SAP_Final_2_0_clean.doc

Author: [name]

Version Number:

2.0

Version Date:

18OCT2018

Template No: CS_TP_BS016 Revision 4

Reference: CS_WI_BS005

Effective Date: 01Apr2016

18.5. PHYSICAL EXAMINATION

Physical examination will not be recorded in the CRF, any findings will appear in medical history or adverse events. The date of physical examination will be listed in a listing.

18.6. OTHER SAFETY ASSESSMENTS

18.6.1. IMMUNOGENICITY PROFILES ANALYSES

The following parameter will be summarized for immunogenicity:

- 1) Total Insulin Antibodies
 - Percent Binding (% B/T)
 - Positive/Negative
- 2) Cross Reactive Insulin Antibodies
 - Percent Binding (% B/T)
 - Positive/Negative
- 3) Insulin (Drug), Specific Antibodies
 - Percent Binding (% B/T)

Descriptive statistics will be tabulated by treatment and by timepoint for the continuous variables. Change from baseline to post-baseline timepoints will also be presented. The same MMRM model as the primary efficacy analysis (without imputing missing data and excluding the basal insulin dosing time) will be used. Estimates of the means, LSM means (SE and 2-sided 95% CIs) as well as treatment difference at each visit will be presented. Analyses will be done on the Safety Population.

The dichotomous outcomes will be summarized with frequency and percentage at scheduled visits. Treatment comparison will be performed using Fisher's exact test. P-value for the two-sided test will be presented.

Potential immunogenicity effect on local and systematic allergic reaction, hypersensitivity, and severe hypoglycaemia will be explored by summarizing those incidences between the treatment groups among subjects with post-baseline positive response of cross reactive antibodies. The local and system allergic reactions as well as the hypoglycaemia are found directly on the CRF, the hypersensitivity events will be found in the coded adverse events with the following specifications:

- System Organ Class (SOC): Immune system disorders
- High Level Group Term (HLGT): Allergic conditions
- High Level Term (HLT): Allergies to foods, food additives, drugs and other
- Preferred Term (PT): Drug hypersensitivity
- Lower level term (LLT): Drug hypersensitivity

Document: \sasdata\Mylan\Insulin_glargine\SYA22825\Biostatistics\Documentation\SAP\MYL-1501D-3004_SAP_Final_2_0_clean.doc

Author: [name]

Version Number: 2.0

Version Date:

18OCT2018

Template No: CS_TP_BS016 Revision 4
Effective Date: 01Apr2016

Reference: CS_WI_BS005

Analysis Plan Template

The possible insulin neutralization effect will also be explored by presenting:

- The incidence of patients with increase over 10% in cross reacting antibody from baseline at any visit
- The incidence of patients with increases of HbA1c over 0.2% increase from baseline at any visit
- The incidence of patients with increase in total or basal insulin dose at any visit.

Treatment group comparisons will be performed by using a Chi-Square test, if 80% of the cells have an expected frequency ≥ 5 otherwise Fisher's exact test will be used.

The immunogenicity and PK data will not be available at the time of database lock for the analysis. However the treatment will remain blinded during the laboratory assay. These data will be locked later and statistical analysis will be performed according to pre-specified method in this SAP.

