5.4 Randomization

Assignment of Subject Identification number (SID), randomization number and study medication, as well as site drug inventory control will be managed by an automated IVRS/IWRS. A manual containing complete instructions for Web or telephone access and use will be provided to each site prior to study start. The IVRS/IWRS will assign a SID for each subject's first clinic visit. Each SID will be unique and serve as the primary subject identifier throughout all phases of the study. The SID must appear on all case report form (CRF) pages, source documents, laboratory data, ECG and diary data. Subjects qualifying to enter the study drug treatment phase, will be assigned an additional "randomization number" by the IVRS/IWRS at randomization. Dynamic allocation with minimization algorithm will be used for treatment randomization. Randomization will be stratified by investigator and basal insulin (Glargine) dose time (morning or evening).

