6.5.2.4 Immunogenicity Assessment

Blood samples of 5 mL each will be taken into serum separator tubes at each time point as outlined in [Table 1](#). At Visits 1, 8, 10, 12, and 14, three blood samples will be drawn, whereas at Visit 6 (baseline) four blood samples will be drawn. The blood samples will be taken by direct venipuncture, and the exact times of blood sampling will be recorded in the CRF. Two of the samples will be used to determine the presence of anti-drug antibodies against insulin glargine using the approach outlined below. The other sample will be collected and stored in reserve for potential supplemental immunogenicity testing and/or characterization. Samples collected pre-dose at the randomization visit (Visit 6) will be considered as baseline. Samples collected at screening and the supplemental samples

collected at baseline may also be used for method development and validation. Sample handling instructions are specified in the laboratory manual.

A conventional radioimmunoassay will be employed for the assessment of anti-drug antibodies in clinical samples. In this assay, samples will undergo a pre-treatment step that includes acid dissociation to release any anti-insulin antibodies complexed with free drug, followed by charcoal adsorption of the free insulin analog. The treated samples will be incubated with a fixed amount of ^{125}I -MYL-1501D, and anti-drug antibody complex formation with the tracer is measured via gamma counter and expressed as a percentage of bound to total radioactivity (%B/T).

The multi-tiered sample analysis recommendations for immunogenicity testing from published white papers [7, 8], and current regulatory guidance [9, 10], will be employed for the immunogenicity assessment of MYL-1501D Process V and Process VI. The antidrug antibody analysis methodology will be fully validated, and the sample analysis procedures will be documented in a Sample Analysis Protocol. Sample handling, processing, and storage instructions will be detailed in a separate manual. The laboratory for immunogenicity analysis will be designated by the Sponsor.

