8. STATISTICAL CONSIDERATIONS

8.1. ADJUSTMENTS FOR COVARIATES AND FACTORS TO BE INCLUDED IN ANALYSES

The following covariates and factors are used in the analyses. For details of their inclusion in the models, see the specific analysis section.

- Pooled sites
- Time of Glargine administration (morning, evening), stratification factor.
- Baseline HbA1c (continuous variable)

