Then, the remaining monotone missing data will be imputed using sequential regression multiple imputation, where a separate regression model is estimated for imputation of each variable (i.e., measurement at each visit) one after the other including the observed values and the values just imputed from the previous visit. Each regression model will include explanatory variables for pooled investigational sites, basal insulin dose time (morning vs. evening), treatment group and all previous (baseline (visit 6), week 12 (visit 12) and week 18 (visit 14)) values of HbA1c.

No rounding or range restrictions will be applied.

Imputed data will consist of 100 imputed datasets. The random seed number for the partial imputation with the MCMC method will be 20171220, and the random seed number for the sequential regression MI will be 171016.

Each of the 100 imputed datasets will be analyzed using the following analysis method. Change from baseline in HbA1c to each post-baseline visit will be calculated based on observed and imputed data. Mean changes from baseline in HbA1c values will be analyzed using a mixed model for repeated measures (MMRM) approach. Restricted maximum likelihood (ReML) estimation will be used. The MMRM model will include the changes from baseline in HbA1c values as dependent variables, the baseline HbA1c values as fixed covariate, pooled investigational sites, basal insulin dose time (morning vs evening), treatment group (MYL 1501D Process V and MYL 1501D Process VI), visit (week 12 and week 18), and treatment group by visit interaction as fixed effects, and subjects as random effect. An unstructured covariance structure will be used to model the within-subject error and the Kenward-Roger approximation will be used to estimate the degrees of freedom. If this analysis fails to converge, the following covariance structures will be tested: AR(1), ARH(1), CS, CSH, TOEP, TOEPH. The covariance structure converging to the best fit, as determined by Akaike's information criteria (AIC) will be used as the primary analysis.

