16.2.3.2. Analysis of change from baseline in fasting plasma glucose

Descriptive statistics will be presented for actual and change from baseline to scheduled visits for fasting plasma glucose. A separate analysis will be done with excluding data with non-fasting status.

Treatment group comparison will be done using the MMRM model as used for the primary endpoint (without imputing missing values), including treatment, visit, treatment-by-visit interaction, pooled-site, basal insulin dosing time, as fixed effects, baseline values as covariate and subjects as random effect.

LSMeans for each treatment group, as well as associated SE and 2-sided 95% CI will be provided by visit. Differences in LSMeans will be calculated and associated 2-sided 95% confidence intervals and p-values will be provided for each visit.

For graphical display at scheduled visits the mean and SD plot will be prepared for the actual plasma

Document: \sasdata\Mylan\Insulin_glargine\SYA22825\Biostatistics\Documentation\SAP\MYL-1501D-3004_SAP_Final_2_0_clean.doc

Author: [name]

Version Number:

2.0

Version Date:

18OCT2018

Template No: CS_TP_BS016 Revision 4

Reference: CS_WI_BS005

Effective Date: 01Apr2016

Analysis Plan Template

glucose measurement by visit and treatment group; LSMeans and 2-sided 95% CI from the same MMRM model will similarly be displayed graphically.

16.2.3.3. Analysis of Change in Daily insulin dose per unit body weight (mealtime, basal insulin and total) for days of 8-point profiles.

Descriptive statistics will be tabulated by treatment and by timepoint. Change from baseline to post-baseline timepoints will also be presented for insulin dose including daily basal insulin dose, daily meal time insulin dose, and daily total insulin dose.

These secondary efficacy parameters will be analyzed using the same MMRM model as the primary efficacy analysis (without imputing missing values). Estimates of the means, LSMeans (2-sided 95% CIs) as well as treatment difference at each visit will be presented.

A graphical display at scheduled visits with the mean and SD plot will be prepared for each of these secondary efficacy endpoints by visit and treatment group; LSMeans and 2-sided 95% CI from the same MMRM model will similarly be displayed graphically.

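### SAP 18.6.1 drops glargine dosing time, a randomization factor, from the percent-binding MMRM without a reason and leaves the baseline covariate unnamed

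*SAP*

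**What the plan says.** Protocol 5.4 describes dynamic allocation by minimization and states: "Randomization will be stratified by investigator and basal insulin (Glargine) dose time (morning or evening". SAP 8.1 lists dosing time as a stratification factor, next to pooled sites and one baseline covariate, "Baseline HbA1c (continuous variable".

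The primary MMRM in SAP 16.1.3 has "the baseline HbA1c values as fixed covariate, pooled investigational sites, basal insulin dose time (morning vs evening", together with treatment, "visit (week 12 and week 18), and treatment group by visit interaction as fixed effects".

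For percent binding, SAP 18.6.1 applies the primary MMRM by reference, "without imputing missing data and excluding the basal insulin dosing time". It names two departures from the primary model, no imputation and no dosing time. It gives no reason for the second, and it mentions neither the baseline covariate nor the visits.

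Antibody sampling follows Protocol 6.5.2.4: "At Visits 1, 8, 10, 12, and 14, three blood samples will be drawn, whereas at Visit 6 (baseline) four blood samples will be drawn". In the schedule of activities, the post-baseline visits among these are weeks 2, 6, 12 and 18. Protocol 7.3 leaves the details of these analyses to the SAP.

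**The concern.** A model normally includes the factors used to balance the allocation. Here one of the two, investigator, stays as pooled site, and the other is removed by name. Immunogenicity heads the list of other objectives and of safety endpoints, so its model should be at least as well specified as those around it.

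The silence on the baseline covariate is the second matter. Taken word for word, the reference to the primary model puts baseline HbA1c into a model for antibody binding. Baseline %B/T, measured at Visit 6 and likely to be the better predictor of later binding, would then be left out.

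Timing adds some weight. SAP 18.6.1 says the immunogenicity data will be locked after the main database. SAP 4.1 has the randomization code requested once the database is locked. An open choice of covariate could therefore be settled after treatment codes are known.

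**Working it through.** **The plan's own figure.** The only powered figure concerns HbA1c (Protocol 7.1): difference 0.03, SD 0.74, margin 0.4, two-sided 95% interval, 90% power. The normal formula gives n per arm = 2 × 0.74² × (1.960 + 1.282)² / (0.4 − 0.03)² = 84.1, so 85. With the t distribution, 85 per arm gives 89.99% power and 86 gives 90.3%, which matches the stated 86 per arm (172). 172 / 0.85 = 202.4, against 202 stated. No sample size, SD or precision is given for antibody binding, so this figure does not bear on the comparison at issue.

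**How the other models treat dosing time and baseline.**

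| Analysis | Dosing time | Baseline covariate |
|---|---|---|
| Primary HbA1c (SAP 16.1.3) | kept | baseline HbA1c |
| HbA1c by visit (SAP 16.2.3.1) | kept | baseline values |
| Fasting glucose (SAP 16.2.3.2) | kept | baseline values |
| Insulin dose, SMBG (SAP 16.2.3.3, 16.2.3.4) | kept, by reference to the primary model | not restated |
| Laboratory, vital signs (SAP 18.2, 18.4; Protocol 7.5.3, 7.5.1) | kept | baseline value (protocol) |
| Hypoglycemia rate (SAP 18.6.2) | kept, by reference | not restated |
| Percent binding (SAP 18.6.1) | **excluded** | **not stated** |

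The fasting-glucose section invokes the primary model and then spells it out with "basal insulin dosing time, as fixed effects, baseline values as covariate and subjects as random effect". The primary model's visit term covers weeks 12 and 18 only, so it cannot apply literally to antibody data from weeks 2, 6, 12 and 18. The reference in 18.6.1 therefore needs interpretation in any case.

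**Cost of omitting dosing time.** For a balanced factor that explains a share R² of the residual variance, the SE ratio is 1/√(1 − R²). R² is an assumption.

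- R² = 0: 1.000
- R² = 1%: 1.005
- R² = 2%: 1.010
- R² = 5%: 1.026

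**Cost of HbA1c in place of baseline %B/T, if that is what is fitted.** Assume equal variance σ² at baseline and follow-up, correlation ρ between them, and HbA1c unrelated to binding. The variance of change is then 2σ²(1 − ρ). After adjustment for own baseline it is σ²(1 − ρ²). The SE ratio is √[2(1 − ρ)/(1 − ρ²)] = √[2/(1 + ρ)]. ρ is an assumption.

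- ρ = 0.5: 1.155
- ρ = 0.8: 1.054
- ρ = 0.9: 1.026

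**Check by simulation.** This used a single visit, ordinary least squares, n = 219 (the sum of the pooled-site table in SAP 8.2), an assumed 30% in one dosing-time stratum, and 1,000 runs per scenario. With own baseline fitted, omitting dosing time gave ratios of 1.010 to 1.011 at R² = 2% and 1.025 to 1.027 at R² = 5%. With HbA1c fitted and R² = 0, the ratios were 1.153, 1.055 and 1.026 for ρ = 0.5, 0.8 and 0.9. With both departures, the range ran from 1.026 (ρ = 0.9, R² = 0) to 1.177 (ρ = 0.5, R² = 5%).

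**The case against.** The strongest reply is that this is a stable, pre-specified choice in an unpowered safety model. The same exclusion stands in SAP V1.0, and the protocol hands the details to the SAP. Covariates also vary elsewhere: the PK model lists no site term, and the non-compliance ANOVA uses only treatment and pooled site. Nothing in the documents says that dosing time predicts antibody binding. If it does not, the loss is nil. A one-line rationale would end the silence. All of this stands as to size. It does not supply the missing reason, and those two analyses are not MMRMs.

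A reader might also infer that the model definitely adjusts for baseline HbA1c. The documents do not support that. Section 18.6.1 names no covariate, the fasting-glucose section and the protocol's laboratory and vital-sign models use the endpoint's baseline, and the visit term shows that the reference is not literal. The same shorthand serves several other endpoints, so this gap is not peculiar to immunogenicity.

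A reader might further infer that the antibody intervals are badly calibrated or the estimate biased. Omitting a balanced factor leaves the estimate unbiased and makes the interval, if anything, slightly conservative.

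**Conclusion.** The point holds in limited form. The unexplained removal of a randomization factor is in the text. The baseline covariate is under-specified, not fixed as HbA1c.

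The size is small on the first count: an SE 0 to 2.6% larger for R² of 0 to 5%, with no bias. On the second count it is about 3 to 15% larger for ρ of 0.9 to 0.5, and only if HbA1c were fitted. These ranges rest on assumed R² and ρ, equal variances, HbA1c unrelated to binding, and a single-visit formula. The documents give nothing from which the actual loss could be derived, so a claim that the antibody comparisons are materially imprecise would go beyond them.

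Percent binding is a secondary safety endpoint with no margin or power. The positive/negative antibody comparisons use Fisher's exact test and are untouched. The HbA1c non-inferiority conclusion is unaffected. The change is still worth making, because it brings the model into line with the randomization and closes an open choice at almost no cost.

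**What to change.** In SAP 18.6.1, delete the words that exclude basal insulin dosing time, and write the model out in place of the cross-reference. The terms would be:

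- fixed effects for treatment, visit (weeks 2, 6, 12 and 18), treatment by visit, pooled site and basal insulin dosing time;
- baseline %B/T of the antibody parameter being analysed as covariate;
- no imputation, as now.

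Make the change before treatment codes are released, since the immunogenicity data are locked after the main database. The cost is SAP wording and one degree of freedom for the binary dosing-time factor. No new data are needed: dosing time is recorded for allocation, and baseline binding is sampled at Visit 6.

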The aim of this study is to demonstrate similar efficacy and safety between MYL-1501D product produced from two manufacturing processes in combination with insulin lispro in patients with T1DM.

Since the two investigational products have an identical presentation of prefilled pen to be used by the subjects during the treatment period, the subject and the treating physician will remain blinded to treatment assignment. Furthermore, the evaluation of the study endpoints, such as analysis of immunogenicity and glycosylated hemoglobin (HbA1c), will be performed in a blinded manner by blinded personnel. The sponsor team as well as the CRO team will also be blinded to the subject assigned treatment.

To ensure that both treatment arms are comparable at baseline with respect to drug-induced immune responses and other parameters, only subjects who have been on a stable dose of Lantus® for at least 3 months prior to screening will be included.

During the 4-week run-in period with Lantus® and Humalog®, the dose of insulin will be titrated (if required) to ensure diabetes control. The run-in period ensures comparable drug exposure for all subjects, and increases the likelihood of comparable immune responses at the start of the treatment period. An 18-week treatment period is an adequate period to detect differences in HbA1c of the treatment arms [5].

Dosing with MYL-1501D during treatment period and Lantus® during run-in period will be guided by self-monitored blood glucose (SMBG)-based glucose level assessments and by the titration committee as detailed in the insulin monitoring (titration committee) plan.

Rescue criteria based on HbA1c are defined based on week 12 HbA1c measurement, so that a potential worsening of metabolic control in subjects during the study can be identified and therapy modified at the discretion of the investigator.

A follow-up visit, 2 weeks after the end of treatment, will ensure the safety of all subjects after they stop the study medication and return to receiving approved medications.

Complete information for the study medication can be found in MYL-1501D Investigator's Brochure (IB). [6]

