7.1 Sample Size Determination

A total of 202 subjects with T1DM are planned to be randomized for this study and will receive either MYL-1501D Process V product or MYL-1501D Process VI product, in a 1:1 ratio.

The sample size estimation is based on assumptions for the change from baseline up to week 18 in HbA1c with either MYL-1501D product from Process V or Process VI. It is assumed, that true mean groups mean difference is 0.03 and standard deviation is equal to 0.74. To demonstrate non-inferiority margin of 0.4% using a 2-sided 95% confidence interval and a 90% power, a total of 172 subjects (86 subjects per treatment group) are required.

To account for a maximum of 15% of subjects being not eligible for the per protocol analysis, a total sample size of 202 is planned to be randomized for this study. The true treatment difference and standard deviation is based on previous study MYL-GAIA-3001.

No replacement of subject will be performed if subject discontinued prematurely from the study.

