7.3 Secondary Endpoints

The following efficacy measures (both actual and change values) will be summarized at baseline and scheduled visit. Similar statistical analysis approach for primary will be performed for continuous variables without imputing missing values. Contrasts of LS mean at each scheduled visit will be used to evaluate all pairwise treatment comparisons, and 95% confidence intervals for treatment differences in LS means will be computed for each visit.

- Change in fasting plasma glucose from baseline
- Change in basal insulin, meal-time, and total insulin dose per unit body weight (U/kg) from baseline
- Change in 8-point SMBG profile from baseline.

All above analyses will be performed on ITT set.

The following safety measures (both actual and change values) will be summarized at baseline and scheduled visit. Contrasts of LS mean at each scheduled visit will be used to evaluate all pairwise treatment comparisons, and 95% confidence intervals for treatment differences in LS means will be computed for each visit. For categorical data analyses, Fisher's exact test or Chi-squared test will be used. The details will be provided in the SAP.

- Incidence of positive antibody response and change in antibody percentage binding from baseline.
- Change in hypoglycemia rate (30 day adjusted) from baseline and incidence of hypoglycemic events
- Incidence of treatment-emergent adverse events (TEAEs) and serious adverse events (SAEs)
- Incidence of local allergic reactions, systemic allergic reactions and other adverse events
- Incidence of device-related safety assessment

The incidence of subjects with each of the three following criteria will be summarized descriptively (for categorical measures) by treatment to explore possible insulin neutralization effect:

- An increase of over 10% in cross reacting antibodies from baseline
- Increases in HbA1c of over 0.2% from baseline at any visit
- Increase in total or basal insulin dose at any visit

The total incidence of Device-related safety events will be summarized for each treatment group and would include device-related TEAEs and events related to device complaints or failures. For device-related TEAEs, two categories will be summarized for each treatment: needle-related TEAEs such as pain, bruise, and bleeding; and other device-related TEAEs, such as hyperglycemia or hypoglycemia. For confirmed device-related malfunctions or failures, incidence will be listed and summarized for each treatment.

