7.5. STATISTICAL TESTS

The default significant level will be (5%); confidence intervals will be 95% and all tests will be two-sided, unless otherwise specified in the description of the analyses.

Non-inferiority will be tested at 2.5% (one-sided) level of significance.

Document: \sasdata\Mylan\Insulin_glargine\SYA22825\Biostatistics\Documentation\SAP\MYL-1501D-3004_SAP_Final_2_0_clean.doc

Author: [name]

Version Number:

2.0

Version Date:

18OCT2018

Template No: CS_TP_BS016 Revision 4
Effective Date: 01Apr2016

Reference: CS_WI_BS005

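### Antibody positivity and adverse event incidence are compared by percentages and a p-value, with no interval for the difference in proportions, although the study aims to demonstrate similar safety

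*SAP*

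**What the plan says.** Protocol V2.0 section 2.2 states the purpose: "The aim of this study is to demonstrate similar efficacy and safety between MYL-1501D product produced from two manufacturing processes". Incidence of positive antibody response is a named safety endpoint (Protocol 3.2.2.1), and immunogenicity, both incidence and relative level, heads the list of other objectives in SAP 3.1.

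For categorical data, Protocol 7.3 says that Fisher's "exact test or Chi-squared test will be used" and leaves the details to the SAP. The 95% intervals it promises are for differences in LS means. The SAP (V2.0) fills in the details:

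- **Antibody status, 18.6.1:** frequency and percentage at scheduled visits, then Fisher's "exact test. P-value for the two-sided test will be presented".
- **Neutralization criteria, 18.6.1:** Chi-square, or Fisher where expected counts are small.
- **Adverse events, 18.1:** Fisher's test with a two-sided p-value.
- **Hypoglycemia incidence, 18.6.2:** no test is named, so only the general rule in Protocol 7.3 applies.
- **Level, 7.5:** "The default significant level will be (5%); confidence intervals will be 95% and all tests will be two-sided, unless otherwise specified". This fixes the confidence level but does not call for an interval on proportions.

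By contrast, HbA1c, fasting glucose, laboratory values, vital signs and percent antibody binding are analysed by MMRM with 95% intervals, and exploratory PK gets a geometric mean ratio with a 90% interval.

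**The concern.** A test of no difference answers a different question from the one the study poses. A small p-value is evidence that the processes differ. A large one may mean that they are alike or that the sample is too small to tell. For the primary endpoint the plan recognises this: non-inferiority of HbA1c is read from a confidence limit. For antibody positivity, where a manufacturing change could plausibly matter, the plan gives a p-value and no statement of which differences the data rule out.

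At stake is what the report can say about immunogenicity incidence and about adverse events. With percentages and a p-value alone, it can say that no significant difference was found. It cannot say that differences above a given size are excluded.

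**Working it through.** **The plan's own sample size.** Protocol 7.1 assumes that the "true mean groups mean difference is 0.03 and standard deviation is equal to 0.74", with a margin of 0.4. The normal approximation per arm is 2 × (1.960 + 1.282)² × 0.74² / (0.40 − 0.03)² = 2 × 10.51 × 4.00 = 84.1, so 85. With the noncentral t distribution, 85 per arm gives 89.99% power and 86 gives 90.3%, which reproduces the stated 86. The 15% allowance gives 172 / 0.85 = 202.4, against 202 stated. The sample size therefore rests on HbA1c alone; no calculation covers a binary safety outcome.

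**Inputs for the check.** 202 randomized 1:1 gives 101 per arm. The level is 5% two-sided (SAP 7.5). Antibody positivity rates are not in the documents, so the control rates below are assumptions shown as a range.

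**Method.** For each control count, find the largest count in the other arm with Fisher p still above 0.05, then take Newcombe's 95% interval for the difference, built from the Wilson limits (l, u) of each proportion:

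lower = d − √[(p₁ − l₁)² + (u₂ − p₂)²]; upper = d + √[(u₁ − p₁)² + (p₂ − l₂)²].

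**Worked example, 64 v 50 of 101.** p₁ = 0.6337 (Wilson 0.5364 to 0.7211); p₂ = 0.4950 (0.3995 to 0.5909); d = 0.1386.

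- Lower: 0.1386 − √(0.0973² + 0.0959²) = 0.1386 − 0.1366 = 0.002.
- Upper: 0.1386 + √(0.0875² + 0.0955²) = 0.1386 + 0.1295 = 0.268.
- Fisher p = 0.065; one more positive (65 v 50) gives p = 0.046, so 64 is the borderline count.

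**Results at 101 per arm** (differences in percentage points):

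| Assumed control rate | Borderline counts | Fisher p | Observed difference | Newcombe 95% interval | Interval if observed rates are equal |
|---|---|---|---|---|---|
| 2% | 9 v 2 | 0.058 | 6.9 | 0.5 to 14.2 | ±5.2 |
| 5% | 14 v 5 | 0.051 | 8.9 | 0.7 to 17.5 | ±6.7 |
| 10% | 20 v 10 | 0.074 | 9.9 | 0.0 to 19.8 | ±8.6 |
| 20% | 33 v 20 | 0.054 | 12.9 | 0.7 to 24.6 | ±11.0 |
| 30% | 44 v 30 | 0.057 | 13.9 | 0.6 to 26.5 | ±12.5 |
| 40% | 54 v 40 | 0.066 | 13.9 | 0.1 to 26.9 | ±13.3 |
| 50% | 64 v 50 | 0.065 | 13.9 | 0.2 to 26.8 | ±13.5 |
| 60% | 75 v 61 | 0.051 | 13.9 | 0.9 to 26.2 | ±13.3 |
| 70% | 83 v 71 | 0.068 | 11.9 | 0.1 to 23.3 | ±12.5 |

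Over control rates of 20% to 70% the borderline upper limit is about 23 to 27 points. It is 25 to 29 at 86 per arm. It is 23 to 26 at 110 per arm, which is roughly half of the 219 subjects that the pooled-site table in SAP 8.2 adds up to.

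**Power of Fisher's test at 101 per arm, by enumeration.** 20% v 30%: 32%. 30% v 40%: 27%. 50% v 60%: 27%. 50% v 65%: 54%. 50% v 70%: 80%. 50% v 75%: 95%.

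**The case against.** The strongest reply is that these are not confirmatory outcomes. The one formal hypothesis is HbA1c non-inferiority, the sample was sized for that alone, the other objectives are only to compare the processes, and there is no multiplicity adjustment. Counts and percentages by arm will be in the tables, so any reader can compute an interval. Percent binding, the other half of the immunogenicity objective, is already estimated with intervals.

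Much of that is true, and it limits the point. A reader might infer that the SAP treats p > 0.05 as proof of similarity; no sentence in either document says so. A reader might also infer that the immunogenicity question goes unanswered. That is too strong, because percent binding is estimated. What remains is the separately named incidence endpoint, for which the only planned inference is a test that cannot address the stated aim. Leaving the interval to the reader is a weak substitute for planning it.

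Two further objections concern the remedy. Without a margin, an interval supplies no pass or fail criterion. And in most of the borderline examples above, the Newcombe interval excludes zero while Fisher's p exceeds 0.05, so the two can disagree. Both are correct. The interval shows which differences are excluded, no more, and the text should say how such disagreement is to be read.

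**Conclusion.** The point stands as a gap in reporting and interpretation. The plan names antibody incidence as an endpoint in a study meant to show similar safety, then specifies no estimate with an interval for it or for any other difference in proportions. The primary analysis is unaffected.

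The size depends on the assumed event rate and on about 101 per arm. It would be tempting to say that any non-significant result leaves room for a 25-point gap. The figures do not support that: limits near 25 points belong to results just short of significance at common rates. Equal observed rates are much tighter, and a true 50% v 75% gap would be detected about 95% of the time. Nor does the figure carry over to rare outcomes, where rates of 2% to 10% give borderline limits of about 14 to 20 points. The low power applies to differences of about 10 points; at 15 points (50% v 65%) it is already 54%.

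**What to change.** In SAP 18.6.1, for antibody positivity and the neutralization criteria, add the risk difference (Process VI minus Process V) with a two-sided 95% score-type interval, naming one method (Miettinen-Nurminen or Newcombe). Do the same for the key binary safety outcomes in 18.1 (any TEAE, any SAE, allergic reactions) and for hypoglycemia incidence in 18.6.2. Add two sentences: similarity will be described by the differences that the interval excludes, and a non-significant p-value is not evidence of similarity. Keep the existing tests as supportive, and say that the interval governs the description where the two disagree.

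The cost is one extra table column, a small programming change, and occasional mild disagreement between interval and Fisher p-value. No new data or larger sample is needed. Protocol section 7 lets the SAP modify planned analyses and requires an amendment only for major changes to the primary endpoint or its analysis, so a SAP revision suffices. It should be made before treatment is unblinded for the main analysis, since SAP 18.6.1 has the immunogenicity data locked after that database.
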